3.3. NULL HYPOTHESIS

3.3.1. For Interleukin-6 (IL-6) levels:

Null Hypothesis:

There is no significant difference in the mean serum level of Interleukin-6 (IL-6) before and after 3 months of *Kelulut* honey consumption among patients with juvenile-onset open-angle glaucoma (JOAG).

3.3.2. For retinal nerve fiber layer (RNFL) thickness:

Null Hypothesis:

There is no significant difference in the mean retinal nerve fiber layer (RNFL)

thickness before and after 3 months of *Kelulut* honey consumption among patients with juvenile-onset open-angle glaucoma (JOAG).

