3.1.2. SPECIFIC OBJECTIVES

1. To compare the mean serum level of Interleukin-6 in patients with JOAG with and without honey Kelulut consumption for 3 months.
2. To compare the mean retinal nerve fiber layer thickness in patients with JOAG with and without honey Kelulut consumption for 3 months.

3. To compare the tear break-up time (TBUT) and Schirmer test in patients with JOAG with and without honey Kelulut consumption for 3 months.

4. To compare the level of glycated hemoglobin (HbA1c) level in patients with JOAG with and without honey Kelulut consumption for 3 months.

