3.2. RESEARCH QUESTIONS

- 3.2.1. Does the mean serum level of interleukin-6 differs with and without

consumption of honey Kelulut for 3 months among JOAG patients?

3.2.2. Does the mean thickness of retinal nerve fiber layer increases with consumption of honey Kelulut for 3 months among patients with JOAG?

3.2.3. Does the tear break-up time (TBUT) and Schirmer test increases with consumption of honey Kelulut for 3 months among patients with JOAG?

3.2.4. Does the level of glycated hemoglobin (HbA1c) increases with consumption of honey Kelulut for 3 months among patients with JOAG?

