3.2. RESEARCH HYPOTHESIS

3.2.1. The mean serum level of Interleukin-6 reduces after consumption of honey Kelulut for 3 months among patients with JOAG.

3.2.2. The mean thickness of retinal nerve fiber layer increases after consumption of Honey Kelulut for 3 months among patients with JOAG.

3.2.3 The tear break-up time (TBUT) and Schirmer test increases after consumption of honey Kelulut for 3 months among patients with JOAG.

3.2.4 The level of glycated hemoglobin (HbA1c) does not increase with the consumption of honey Kelulut for 3 months among patients with JOAG.

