3.3.3 For dry eye disease parameters

Null Hypothesis:

There is no significance difference in tear break-up time (TBUT) and Schirmer test increases after consumption of honey Kelulut for 3 months among patients with juvenile-onset open-angle glaucoma (JOAG).

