3.3.4 For level of glycated hemoglobin

Null Hypothesis:

There is no significance difference in the level of glycated hemoglobin level after consumption of honey Kelulut for 3 months among patients with juvenile-onset open-angle glaucoma (JOAG).

CHAPTER 4: METHODOLOGY

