4.4. SAMPLE SIZE

Sample size calculation

GPower 3.1.9.7 software was used to calculate the sample size.

The power of the study will be set at 80% with a significance level of 5%.

For the sample size calculation was statistical data used was repeated measures ANOVA within and within between.

The largest sample size was 24.

To account for the attrition rate, 20% was added, which gives a total estimated minimum sample size of 30 per group.

Total sample size: 60 (30 per group)

Objective 1:

To compare the mean serum level of Interleukin-6 before and after consumption of honey Kelulut for 3 months among patients with JOAG.

Calculated sample size: 24

By the addition of 20% drop outs, the sample size that needs to be collected for each group is 30 subjects

Total sample size: 60

Objective 2:

To compare the mean RNFL thickness before and after consumption of honey Kelulut for 3 months among patients with JOAG.

Calculated sample size: 24

By the addition of 20% drop outs, the sample size that needs to be collected for each group is 27 subjects.

Total sample size: 60

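### The IL-6 and RNFL null hypotheses and the sample-size objectives are before-after statements about honey, which contradicts the with-versus-without-honey objectives; the protocol does not say which effect decides

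*Protocol*

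**What the plan says.** The protocol describes the comparison in two ways.

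**Between arms.** Specific objective 1 (section 3.1.2) reads "To compare the mean serum level of Interleukin-6 in patients with JOAG with and without honey Kelulut consumption for 3 months". Objectives 2 to 4 (RNFL, TBUT and Schirmer, HbA1c) take the same form. Research question 3.2.1 asks "Does the mean serum level of interleukin-6 differs with and without" honey. Sections 4.1, 4.6 and 4.7 describe a randomised controlled trial with an untreated no-honey group.

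**Before against after honey.** The IL-6 null (3.3.1) is "There is no significant difference in the mean serum level of Interleukin-6 (IL-6) before and after 3 months of" honey consumption. The RNFL null (3.3.2) opens "There is no significant difference in the mean retinal nerve fiber layer (RNFL" and continues with thickness before and after three months of honey. Section 4.4 restates objective 1 as "To compare the mean serum level of Interleukin-6 before and after consumption of honey Kelulut for 3 months among patients with JOAG", and objective 2 likewise for RNFL.

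**No comparator named.** The dry-eye null (3.3.3) reads "There is no significance difference in tear break-up time (TBUT) and Schirmer test increases after consumption of honey Kelulut for 3 months". The HbA1c null (3.3.4) reads "There is no significance difference in the level of glycated hemoglobin level after consumption of honey Kelulut for 3 months". Neither mentions the no-honey group.

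For IL-6 and RNFL, section 4.10.6 plans a repeated-measures ANOVA with both the within and the within-between effects and treats every p-value under 0.05 as significant. The Chapter 5 outcome tables have rows for both arms at both times under titles that speak of pre and post treatment. They have no line for the between-arm difference in change.

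**The concern.** Patients in the no-honey group take no honey, so a null about levels before and after honey concerns the honey arm only. Any change in that arm contradicts it, whatever happened in the controls. The objectives ask whether the honey arm changed differently from the control arm. The two statements can be answered in opposite ways by the same data.

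The analysis section does not settle the matter, because it lists both kinds of effect and does not say which one tests the hypothesis. A report that follows section 3.3 literally could reject the IL-6 null on a change that the controls shared and present it as an effect of honey. The control group would then have no bearing on the conclusion it was included to support.

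**Working it through.** **The plan's own figure.** Section 4.4 gives 24, inflated for 20% dropout: 24 / (1 − 0.20) = 30 per group, as stated. The 24 itself cannot be reproduced, because no effect size, SD or correlation is given. It also does not reveal which contrast was sized. Take, as assumptions, effect size f = 0.30, correlation 0.5 and m = 2 time points. The noncentrality is f²·N·m / (1 − ρ) = 0.09 × 24 × 2 / 0.5 = 8.64. A total of N = 24 then gives power 0.804 for the within effect in one group and 0.802 for the within-between effect in two groups.

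**What each test responds to.** With two time points, work with each patient's change, scaled to SD 1. Let both arms share a true change δ, with no honey effect and n patients per arm. Tests are two-sided at 0.05.

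- Honey-arm before-after test (the null as written): noncentrality δ√n, df n − 1.
- Group-by-time (the objectives): noncentrality (δ − δ)·√(n/2) = 0, so it rejects 5% of the time for any δ if patients are independent.
- Pooled time effect (the within term with both arms in the model): noncentrality δ√(2n), df 2n − 2.

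**Numbers.** The protocol gives no value for δ, so δ = 0.25 is an assumption, shown with a range of 0.1 to 0.5.

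Honey arm, δ = 0.25:
- n = 24: 0.25 × √24 = 1.225, critical t(23) = 2.069, rejection 0.217.
- n = 30: 0.25 × √30 = 1.369, critical t(29) = 2.045, rejection 0.263.

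| Shared drift (SD of change) | Honey-arm test, n=24 | Honey-arm test, n=30 | Group-by-time |
|---|---|---|---|
| 0.1 | 0.076 | 0.083 | 0.05 |
| 0.25 | 0.217 | 0.263 | 0.05 |
| 0.5 | 0.650 | 0.754 | 0.05 |

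A simulation of 100,000 trials with 24 independent patients per arm and drift 0.25 gave 0.217 for the honey-arm test and 0.050 for group-by-time.

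**The pooled time effect.** At δ = 0.25 it rejects 0.396 of the time with 24 per arm and 0.478 with 30 per arm. It averages over patients who took no honey, so it is not itself a test of the nulls in 3.3.1 and 3.3.2. These figures show only what happens if that effect is misread as an effect of honey.

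**Direction.** The nulls as written have no direction, so a drift either way rejects them at the rates above. Research hypothesis 3.2.1, however, predicts a fall in IL-6, so only a downward drift could pass for a benefit. For RNFL the only drift in the protocol is normal ageing (section 2.4): 0.54 µm per year × 3/12 = 0.135, about 0.14 µm of thinning in three months. Hypothesis 3.2.2 predicts an increase, so this drift works against a false claim.

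**The case against.** The strongest reply is that the right comparison is already planned. The trial is randomised with a no-honey arm, section 4.10.6 names the within-between effect, and the Chapter 5 tables set the two arms side by side. Which ANOVA term decides is often left to an analysis plan, and that plan is not at hand. No IL-6 drift is documented either. The same kit and machine are used at both visits (4.10.1, 4.10.7) and serum is kept at −70 °C or lower (4.10.2).

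Much of this stands. It limits the consequence and means that nothing in the analysis has to be invented. It does not remove the contradiction: the protocol states a null that differs from its own objectives, and that is not a detail deferred to another document.

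Some stronger readings are tempting but are not supported:

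- *The study is underpowered because 24 came from a before-after test.* Section 4.4 names both within and within-between, calls 24 the largest result and gives no effect size. If only the honey arm changes, the time and group-by-time effects have the same noncentrality, δ√(n/2), and so equal power. No power loss is shown.
- *The false-claim rate is about 10% without any drift, because either ANOVA effect could be used.* That counts results in both directions. Counting only the predicted direction, simulation puts it at about 5%. With an upward IL-6 drift of 0.25 SD, a favourable result on either effect occurs only about 2.5% of the time.
- *The pooled 40% and 48% are rejection rates of the stated null.* They are not, for the reason given in the working.
- *RNFL is as exposed as IL-6.* The only documented drift points the other way.

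**Conclusion.** The point holds as a contradiction in the current text. The IL-6 and RNFL nulls and the objectives in 4.4 are before-after, the specific objectives and the IL-6 research question are between-arm, and the dry-eye and HbA1c nulls name no comparator. Of the two effects in 4.10.6, only within-between answers the objectives, and the protocol does not say that it decides. It should be fixed, but it does not invalidate the design.

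That a shared change rejects the null as written is a matter of logic and needs no number. Its size is illustrative: 22% at n=24 and 26% at n=30 for a drift of 0.25 SD, and 8% to 65% at n=24 for 0.1 to 0.5 SD, against 5% for group-by-time. These figures rest on an unsourced drift, no honey effect and independent patients. They amount to false benefit claims only if the drift runs in honey's favour. The practical concern is IL-6; for RNFL the issue is consistency of wording.

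**What to change.** - **3.3.1:** restate as *no difference between the honey and no-honey groups in mean change in serum IL-6 from baseline to 3 months*. Use the same form for 3.3.2 (RNFL), 3.3.3 (TBUT and Schirmer) and 3.3.4 (HbA1c).
- **4.4:** restate both objectives in the same between-arm form.
- **4.10.6:** state that only the group-by-time contrast, that is the between-arm difference in change, supports a claim about honey, and that within-arm changes are descriptive.
- **Chapter 5:** add to each outcome table the between-arm difference in change with its 95% CI.

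The cost is wording in three sections and one line per table, with no added patients, visits or measurements. The downside is that a within-arm change can no longer support a claim. The fix removes only drift common to all centres. Section 4.6 assigns whole centres to arms, so clustering by centre and centre-specific drift remain; they are a separate issue, and the 5% level quoted for group-by-time does not allow for them.

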3.3.3 For dry eye disease parameters

Null Hypothesis:

There is no significance difference in tear break-up time (TBUT) and Schirmer test increases after consumption of honey Kelulut for 3 months among patients with juvenile-onset open-angle glaucoma (JOAG).

3.3.4 For level of glycated hemoglobin

Null Hypothesis:

There is no significance difference in the level of glycated hemoglobin level after consumption of honey Kelulut for 3 months among patients with juvenile-onset open-angle glaucoma (JOAG).

CHAPTER 4: METHODOLOGY

4.1. STUDY DESIGN

Randomised controlled trial

4.2. STUDY POPULATION, LOCATIONS AND DURATION

Study population:

Patients diagnosed with Juvenile Open Angle Glaucoma (JOAG)

Study site:

Department of Ophthalmology Hospital Universiti Sains Malaysia (HUSM)

Department of Ophthalmology Hospital Raja Perempuan Zainab II (HRPZ II)

Department of Ophthalmology Hospital Sultanah Nur Zahirah (HSNZ)

Department of Ophthalmology Hospital Sultan Ismail Petra (HSIP)

Co-researchers:

[name] [name] MPM 34859 (HUSM)

[name] [name] MPM 39594 (HRPZ II)

[name] [name] MPM 33552 (HSNZ)

[name] [name] MPM 49484 (HSIP)

Study site involves patients from the Department of Ophthalmology attending Glaucoma follow up clinic, under the supervision of Glaucoma Specialist. These centers have the appropriate expertise, facilities and patient populations.

All recruited patients are managed by trained Glaucoma specialists following a standardized protocol for the administration of Kelulut honey, clinical assessments, and data collection to minimize inter-site variability. Further measures include standardize procedures for IL-6 sample collection, RNFL imaging, and standardized clinical evaluations across all sites.

Study duration:

Febrary 2026– June 2026

End point: Completion of honey supplement for 3 months, followed by comprehensive ophthalmic examination, blood sampling collection and OCT RNFL measurement.

4.3. SAMPLING METHOD

Sampling method

1. All JOAG patients that fulfilled selection criteria
2. Patients who are treated at Ophthalmology Clinic HUSM, HPRZ II, HSNZ and HSIP from February 2026 – November 2026.

4.4. SAMPLE SIZE

Sample size calculation

GPower 3.1.9.7 software was used to calculate the sample size.

The power of the study will be set at 80% with a significance level of 5%.

For the sample size calculation was statistical data used was repeated measures ANOVA within and within between.

The largest sample size was 24.

To account for the attrition rate, 20% was added, which gives a total estimated minimum sample size of 30 per group.

Total sample size: 60 (30 per group)

Objective 1:

To compare the mean serum level of Interleukin-6 before and after consumption of honey Kelulut for 3 months among patients with JOAG.

Calculated sample size: 24

By the addition of 20% drop outs, the sample size that needs to be collected for each group is 30 subjects

Total sample size: 60

Objective 2:

To compare the mean RNFL thickness before and after consumption of honey Kelulut for 3 months among patients with JOAG.

Calculated sample size: 24

By the addition of 20% drop outs, the sample size that needs to be collected for each group is 27 subjects.

Total sample size: 60

4.5. SELECTION CRITERIA

Inclusion criteria

All JOAG patients age 15 years old and above – 40 years old at the time of diagnosis

Compliant to conventional treatment and achieved target intraocular pressure

Exclusion criteria

Patients with allergy to honey or honey-based products

OCT signal less than 6/10

Concurrent retinal diseases and other optic neuropathies

Systemic neurodegenerative disease

Systemic comorbidities such as diabetes mellitus and autoimmune diseases

Patients on other honey-based products for the last 3 months

Patient who consumes honey-based products during the study duration of 3 months

(monitoring via honey-diary, return of the used sachet during the follow up visits)

Patients on anti-oxidants, traditional medications or herbal products for the last 3 months

Topical usage of steroids, systemic steroids and non-steroidal anti-inflammatory drugs.

Sepsis

Compliance less than 75%.

The duration of treatment with honey will be 3 months (90 days), patient who missed more than 22 sachets of honey will be excluded.

Compliance will be assessed through regular monitoring via monitoring of honey-diary and patients are required to return the used honey sachets during clinic visits.

Withdrawal criteria

All patients who do not receive standard treatment for JOAG

All candidates who develops sudden unexpected severe allergic reaction (SUSAR) to the investigated product.

Participants who withdraw or drop out of the study will not be replaced. Follow-up assessments will continue for all participants, including those who withdraw from the honey supplementation, to allow for comprehensive data collection and minimize loss to follow-up. Throughout the study period, participants will continue their conventional glaucoma medications without interruption to ensure standard clinical care is maintained.

4.6. RANDOMISATION

The design for this study includes four centers, with two centers randomly assigned to the treatment “honey” group and the remaining two to the control “no-honey” group.

Individual randomization poses practical limitations due to the rarity of juvenile-onset open-angle glaucoma (JOAG). In this context, such randomization is more feasible and logically advantageous, particularly in terms of coordinating the supply *Kelulut* honey to patients and simplifies distribution of *Kelulut* honey. The *Kelulut* honey is supplied to participants on a monthly basis. During each monthly visit, compliance with the honey

consumption regimen is reviewed, and any potential side effects are systematically monitored and documented. This regular follow-up ensures adherence to the intervention and allows for timely identification of adverse events, thereby enhancing the safety and reliability of the study.

Blood samples for the measurement of serum Interleukin-6 (IL-6) levels will be collected and these samples will then be transported under controlled conditions to the HUSM (Hospital Universiti Sains Malaysia) laboratory for analysis. This ensures a coordinated transportation of blood samples to HUSM laboratory.

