4.10. DATA COLLECTION AND ANALYSIS

4.10.1. PATIENT RECRUITMENT

The study will be conducted after obtaining approval from the Universiti Sains Malaysia Ethical Committee. Patient from the Department of Ophthalmology Hospital Universiti Sains Malaysia (HUSM), Department of Ophthalmology Hospital Raja Perempuan Zainab II (HRPZ II), Department of Ophthalmology Hospital Sultanah Nur Zahirah (HSNZ) and Department of Ophthalmology Hospital Sultan Ismail Petra (HSIP) will be selected according to our inclusion and exclusion criteria. Participants who fulfilled the selection criteria are identified and provided with the information sheet regarding the study. Written informed consent is obtained from all participants or legal guardian.

The eye with the better visual acuity will be selected to standardize the examination. A comprehensive ophthalmic assessment is done which includes visual acuity, Schirmer test, Tear break-up time (TBUT), intraocular pressure measurement by Goldmann applanation tonometry, slitlamp and fundus examination and gonioscopy using Goldmann three mirror contact lens. OCT macula and RNFL thickness measurement using optical coherence tomography is done after pupillary dilatation by some identified single-blinded trained personnel.

Blood sampling will be taken from all participants, serum separated, stored and transported to HUSM Laboratory and assayed. Quantification of cytokine IL-6 performed using IL-6 enzyme-linked immunosorbent assay (ELISA) kit. The participants were randomized into either ‘honey’ or ‘non-honey’ groups. The honey used in this study is Brainer Madu Kelulut, harvested from *Heterotrigona Itama* supplied for a total of three months after the recruitment and completion of initial examination and

blood sampling. The participants in the ‘no honey’ group did not receive any placebo. After 3 months of honey supplement therapy, participants in both groups were reassessed during follow-up. The mean serum IL-6 and RNFL thickness were re-measured, using the same OCT machine and IL-6 ELISA test kit. Participants who were not compliant to the honey supplement were excluded from the study.

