4.10.6. DATA COLLECTION AND ANALYSIS

Data recorded in data collection sheet transferred into electronic data and analyzed using Statistical Package for Social Sciences (SPSS), the latest version. The mean serum IL-6 and mean RNFL thickness of both groups will be analyzed using ANOVA repeated measures; within factors and within-between factors. All the p-value of less than 0.05 was considered statistically significant.

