4.10.7. FOLLOW UP

Patients are assessed after a period of 3 months. RNFL thickness and serum IL-6 level will be measured. All these parameters will be measured using the same machine using same techniques. Compliance to the honey supplement will also be tested, by evaluating the diary filled by the patients and the consumed honey packages. Participants who were found to be less than 75 % compliant with the study were excluded from the study.

CHAPTER 5: RESULTS

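### Four hospitals are randomised, two per arm, but sample size and analysis count patients: a centre-level test of this size does not reach 80% power, and the 5% level holds only without centre effects on change

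*Protocol*

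**What the plan says.** Section 4.6 (Randomisation) states "The design for this study includes four centers, with two centers randomly assigned to the treatment" arm; the remaining two centres form the control arm. It sets individual randomisation aside because the disease is rare and because honey is easier to supply this way.

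Section 4.4 (Sample size) states "The power of the study will be set at 80% with a significance level of 5" per cent. On the method it says "For the sample size calculation was statistical data used was repeated measures ANOVA within and within between", and on the result "The largest sample size was 24". This is raised for 20% dropout to 30 per group, 60 in all. The section gives no effect size, SD, correlation, ICC, design effect or number of clusters.

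Section 4.10.6 fixes the analysis: "The mean serum IL-6 and mean RNFL thickness of both groups will be analyzed using ANOVA repeated measures; within factors and within-between factors", with p below 0.05 as the criterion. It contains no term for centre.

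Section 4.10.1 says "The participants were randomized into either" of the two groups, which does not agree with section 4.6.

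**The concern.** When whole hospitals are allocated, centre is nested in arm. Anything that makes the 3-month change differ between hospitals (case mix, local OCT and tear-film measurement, blood handling, follow-up practice) enters the honey-versus-control contrast directly. Two centres per arm leave only 2 degrees of freedom to estimate that variation. A patient-level analysis ignores it and uses the much smaller within-centre scatter as its yardstick.

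The specific objectives in section 3.1.2 are comparisons with and without honey. A p-value below 0.05 from this plan could therefore reflect a difference between hospitals and be read as an effect of honey. The 80% power is also claimed for a design that was not chosen. An SAP cannot cure this by adding centre as a fixed term, because the arms are made up of different centres.

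**Working it through.** **Inputs from the protocol.** Four centres, two per arm (4.6); 80% power, 5% level, 24 raised to 30 per group (4.4); patient-level repeated-measures ANOVA (4.10.6).

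**Assumptions.** Two-sided 5%. Equal centre sizes, so m = 12 completers per centre (24 per arm) or 15 (30 per arm). ICC of the change score from 0 to 0.10. The 24 comes from the group-by-time test. Both readings of 24 (per group, or the G*Power total) are carried.

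**Step 1: the plan's own figure.** 24/(1 − 0.20) = 30, so the dropout step reproduces and favours the per-group reading. The 24 itself cannot be reproduced, because no effect size is given.

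**Step 2: implied effect.** With two time points, the group-by-time test equals a two-sample t-test on change. Solving the noncentral t for 80% power gives δ = 0.826 SD of change with 24 per arm, and δ = 1.197 SD with 12 per arm.

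**Step 3: power of a test that respects the allocation.** In SD units, a centre mean of change has variance v = ICC + (1 − ICC)/m. With two centres per arm the arm difference has variance v/2 + v/2 = v. The test is a t-test with 2 df (critical value 4.303) and noncentrality δ/√v. Example: δ = 0.826, m = 12, ICC 0 gives 0.826/√(1/12) = 2.86 and power 36%.

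| Effect | m | ICC 0 | 0.01 | 0.05 | 0.10 |
|---|---|---|---|---|---|
| 0.826 SD | 12 | 36% | 34% | 27% | 21% |
| 0.826 SD | 15 | 42% | 39% | 29% | 23% |
| 1.197 SD | 12 | 59% | 55% | 45% | 36% |
| 1.197 SD | 15 | 67% | 62% | 49% | 39% |

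Reaching 80% at ICC 0 takes 47 completers per centre (0.826 SD) or 23 (1.197 SD), against about 15 enrolled. As m grows without limit, v tends to the ICC. Power then cannot exceed 51% (0.826 SD) or 77% (1.197 SD) at ICC 0.05, nor 32% or 53% at ICC 0.10.

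**Step 4: type I error of the planned test.** Simulation of 2 + 2 centres with no honey effect, patient-level test at nominal 5%:

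| Test | m | ICC 0 | 0.01 | 0.05 | 0.10 |
|---|---|---|---|---|---|
| Planned | 12 | 5.0% | 6.3% | 11.7% | 18.2% |
| Planned | 15 | 5.0% | 6.7% | 13.5% | 21.3% |
| With fixed centre term | 12 | 5.0% | 6.3% | 12.2% | 19.4% |
| Four centre means, 2 df | 12 or 15 | 5.0% | 5.0% | 5.0% | 5.0% |

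**Step 5: re-randomisation check.** Four centres allow C(4,2) = 6 allocations, so the smallest possible two-sided re-randomisation p-value is 2/6 = 0.33.

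**The case against.** The strongest reply is that low power belongs to the 2-df test, not to the test the protocol names. At ICC 0 the planned ANOVA is valid and has 80% power with 24 per arm and 88% with 30 (δ = 0.826), or 98% and over 99% if 24 was a total. The protocol also takes steps that may keep centre effects on change small: standardised procedures across sites (4.2), blinded IL-6 processing at one institution (4.10.2, although 4.10.3 names different laboratories), and before-and-after consistency, "All these parameters will be measured using the same machine using same techniques" (4.10.7). The high error rates come from the top of an assumed ICC range; at 0.01 the rate is only 6–7%.

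All of this is correct, and it fixes how the point should be worded: the stated power and level hold only if the ICC of change is exactly zero. The protocol does not claim or justify that. Standardisation can reduce centre effects but does not show that they are absent, and two centres per arm give almost no means of checking.

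A second reply is that the effect is back-derived. If 24 came from the within-patient factor and not from group-by-time, the 0.83 SD has no basis. That would change the power figures. It would not affect the type I error results, and the between-arm comparison would then have no sample-size justification at all.

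**Conclusion.** The concern holds and should be fixed before the trial relies on its between-arm p-values. Section 4.6 randomises centres, sections 4.4 and 4.10.6 count patients, and section 4.10.1 contradicts section 4.6. At the planned size, a centre-level comparison falls short of 80% at every ICC examined, including 0, under both readings of 24: at best 42% per group or 67% as a total. The 5% level of the planned test is not assured; it rises to about 12–14% at ICC 0.05 and 18–21% at 0.10. The sizes depend on equal centres, an assumed ICC range and an effect inferred from 24. The mismatch between design and analysis does not.

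**What to change.** If centre allocation is kept:

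1. **Section 4.4.** Withdraw the 80% claim, say whether 24 is per group or a total, and state power as a range with its assumptions. For example: *two centres per arm with 12–15 completers each give 36–42% power at ICC 0 and 21–23% at ICC 0.10 for a difference of 0.83 SD of change* (59–67% and 36–39% for 1.20 SD if 24 is the total).
2. **Section 4.10.6.** Base the between-arm comparison on the four centre means of change (2 df), or another method that respects the allocation, and report between-arm p-values as exploratory.
3. **Section 4.10.1.** Say that centres, not participants, were randomised.

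This costs wording only and no extra patients, but the stated power falls and the between-arm conclusions become exploratory.

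Two larger options are for the sponsor to weigh:

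- **More centres.** With k centres per arm, noncentrality is δ/√(2v/k) on 2(k − 1) df. At 0.83 SD and 12 completers per centre, 80% needs 4 per arm at ICC 0 to 0.01, 5 at 0.05 and 6 at 0.10, which is 96 to 144 completers. That is hard in a rare disease.
- **Randomising patients 1:1 within each centre, with centre in the model.** This removes the nesting. It needs a protocol amendment and honey supply at four clinics instead of two, and it runs against the rarity and supply reasons in section 4.6. It also risks contamination in an open-label trial without placebo. Because section 1.2 describes the disease as typically autosomal dominant, relatives attending one clinic could be split between arms.
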